Despite HBST’s promise for expanding testing in this high-priority population, many salient concerns remain about its use in real-world settings. Among the more critical of these is that HBST users may not be adequately linked with vital resources after testing, which may result in critical delays in seeking care and additional resources, such as confirmatory testing, testing for other sexually-transmitted infections (STIs), and other prevention resources (e.g., pre-exposure prophylaxis [PrEP], risk reduction counseling)¹¹. Others have also expressed concern about the lack of post-test counseling in HBST^{12,13}. Currently, OraSure® offers a 24-hour helpline that provides test counseling and referrals to local HIV prevention/care services¹³, but this approach is passive and relies on users to “reach out” for these services. Coupling existing and ubiquitous technologies with the delivery of HBSTs can enable a more “active” system for engaging with HBST users after testing to offer prompt follow-up and post-test counseling over the phone. In this “enhanced HBST” system, a mobile monitoring sensor detects when HBST kits are opened, triggering an alarm on dedicated mobile phones carried by qualified HIV test counselors

(QHTC), prompting them to follow up with users over the phone within 24 hours. Conducting active follow-up through “enhanced HBST” may increase the number of HBST users who receive follow-up counseling and are referred/linked with care, confirmatory testing, and additional services. Providing timely follow-up counseling via enhanced HBST could also be an intervention-in-itself that increases the likelihood of future testing. To address this gap in service delivery, this proposal aims to:

Specific Aim 1: Refine technology that enables real-time, remote monitoring of HBST kits, allowing delivery of post-test counseling and service referrals to HBST users over the phone (“Enhanced HBST”). This will be accomplished using an iterative developmental process informed by qualitative methods with target group members to produce a feasible and acceptable system for conducting “active” follow-up after HBST.

Specific Aim 2: Explore whether “enhanced HBST” results in higher rates of (2a) any and repeat testing, (2b) receipt of post-test counseling, and (2c) follow up for additional services (e.g., STI testing, PrEP) versus standard HBST.

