Secondary Aims: We will also explore potential within- and between-subject effects of Enhanced HBST versus standard HBST on positive/negative affect, social support, sex risk behavior, and health empowerment.

Overview of the research: During a “start-up” period of 6 months, we will use qualitative methods (focus group [$N=8$], individual interviews [$N=10$]) to inform ongoing consultation with Devicix (an electrical and software engineering firm) on refining a mobile technology for monitoring HBST use, ultimately preparing it for deployment. Then, during the “study phase,” 40 high-risk MSM in the Providence, RI area will be randomly assigned to one of two conditions: An “enhanced” HBST condition ($N=20$) or standard HBST ($N=20$). In both conditions, 3 HBST kits will be sent by mail at 3-month intervals over the course of 6 months (baseline, 3-months, 6-months). We chose to deliver HBSTs by mail given recent evidence that a majority of MSM prefer this method of receiving kits (as opposed to pharmacy pickup or vending machines)^{50,51}. In the “enhanced” HBST condition, mailed test enclosures will be equipped with a mobile monitoring sensor (see Section 3C.3.1.) that triggers an alarm on dedicated mobile phones carried by qualified HIV test counselors (QHTC). QHTCs will then conduct a follow-up call to the user within 24 hours. In the HBST alone condition, test kits will simply be mailed to participants with contact information for local HIV care, confirmatory testing, STI testing, and PrEP. All participants will be oriented to the study during a baseline, in-person appointment at Brown University. Then, participants will complete monthly assessments online over the course of 7 months while on the study (see Fig. 1 for a timeline). To complete the project within the 2-year period, 4 participants per month will be recruited on a rolling basis (beginning in month 6 of year 1), allowing all participants to finish the study by month 10 in Year 2.

C.2 Participant Population

The research has three phases: (1) Focus group phase [$N = 8$], (2) individual interview phase [$N = 10$], and (3) pilot study phase [$N = 40$]. *All* participants (regardless of which phase they are participating in) will meet the same criteria.

Inclusion criteria are as follows:

1. Biologically male
2. Aged 18 or older

3. Have not been tested for HIV in the last year

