Experimental conditions. In this 7-month longitudinal study, 40 participants will be randomized to receive either “enhanced” HBST ($N=20$) or standard HBST ($N=20$). All will have 3 OraSure® test kits shipped to their homes 1-week after baseline, 3-months, and 6-months. Those in the “enhanced” HBST condition will receive follow-up calls within 24 hours after opening their tests. Those in standard HBST will be provided contact information for local services in their test kits, in addition to the information provided by OraSure®.

Measures. Demographics, past HIV testing history, sexual behavior, and other relevant variables will be collected at baseline. Throughout the 7-month study period, participants will complete online assessments each month inquiring about whether they used a study-provided HBST kits in the last month and what the result was. Items will also assess whether they were provided referral to a local agency for additional prevention services (e.g., additional HIV testing, STI testing, PrEP consultation, HIV risk reduction counseling) by a professional in the last month, and whether they sought each service over the last month. Participants will also complete Timeline Follow Back (TLFB^{55,56}) assessments of their sexual behavior over the past month. The TLFB has proven to be one of the more reliable and valid assessments available for sexual behaviors⁵⁷⁻⁶⁴, and recent evidence suggests that optimal accuracy in reporting may be achieved with short follow-up periods (e.g., 30 days)⁵². Monthly online assessments will also measure general positive/negative affect over that time using the positive and negative affect scales of the PANAS-X⁶⁵, a 20-item scale that asks participants to rate various emotion words according to the extent they have “felt this way over the past month,” on a 1 (*very slightly*) to 5 (*extremely*) scale. These subscales have excellent psychometric properties when used to measure trait affect⁶⁵. Health empowerment will be measured each month using the Patient Activation Measure (PAM-13⁶⁶), and social support will be assessed with 3 subscales of the Received Support Scale (Emotional, Informational, Satisfaction). Both measures have excellent psychometric properties⁶⁶⁻⁶⁹.

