keep their phone near them as much as possible over the 7-month study. They will also be instructed to inform study staff as soon as possible should they lose their phones, change phones, or their current service contract lapses. One week after the initial appointment, an HBST kit will be sent to participants’ verified addresses. Shipment tracking will be used to record data about when HBST participants receive their tests. In “enhanced” HBST, participants, opening their mailed test enclosure will trigger an alert on the study database, which is monitored regularly by staff QHTCs. These alerts will instruct QHTCs to conduct a follow-up call with participants. QHTCs will be CAAS postdoctoral trainees with Ph.D.’s in clinical psychology who have completed additional training in HIV testing counseling (offered by [name]), suicide prevention intervention (offered by nearby Lifespan Hospital), and study-specific follow-up procedures. QHTCs will take turns placing follow-up calls. QHTCs will conduct calls while in private offices on Brown University’s campus. As such, they will be able to access the study database while conducting the calls, so as to allow check-ins about previous referrals and data entry during calls. QHTCs will follow up with participants within 24 hours after the test is opened. During follow-up calls, QHTCs will verify whether the participant has completed the test, what the result was, and ask whether the participant would like to receive counseling, entering this data into the study database. For reactive results, QHTCs will facilitate appointments for confirmatory testing. For non-reactive results, QHTCs will inquire about participants’ interest in other prevention services (e.g., STI testing, counseling). QHTCs will also screen for suicidality and record this information using the data entry forms, providing intervention/referral if needed. If participants indicate they have not taken the test yet but plan to do so, QHTCs will ask when they plan to take the test and whether there is a better time to contact them again. If a participant cannot be reached during the 24-hour post-test window, the 3 additional follow-up attempts will be made over the following 72 hours. This process will repeat for tests sent at 3 and 6 months. To facilitate monthly study assessments, participants will receive an email with a link to an each assessment specific to that participant and time period. Participants will be asked to complete these on a desktop computer within 2 days of receipt, and failing to do so within that time will prompt the RA to follow up via phone and email to encourage adherence. Once the study is complete, the RA will follow-up with participants over the phone to conduct a 30-minute qualitative interview. This interview will assess participants’

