STUDY PROTOCOL

Title: Exploring Use of a Real-time, Remote Monitoring and Follow-up System for Home-based, HIV Self-testing Among High-risk Men Who Have Sex With Men (MSM)

NCT#: NCT02876926

Date of document: Last reviewed and approved by Brown IRB on 9/15/18

Analysis plan. Monthly survey responses were first aggregated across the entire study period for each of the study's key outcomes: HIV testing rates, STI testing rates, receipt of risk reduction counseling, receiving prevention supplies, PrEP referrals, and being prescribed PrEP. Linear or Poisson regression models with planned contrasts were then used to explore differences in these outcomes between the study groups across the entire 7-month study period. Next, we used survey completion dates to examine rates of each outcome across the 3-month study intervals (baseline, 3-months, and 6-months), which align with current CDC recommendations for HIV testing every 3-6 months among high-risk MSM. Repeat testing was defined as having tested at least twice in at least two of these intervals over the course of the study period. To explore the effect of condition outcomes over time, we used generalized estimating equations (GEE) with binomial distributions and logit-link functions for binary outcomes, and Poisson distributions and with log-link functions for count outcomes. All models were analyzed using an intent-to-treat (ITT) approach that involved retaining participants who withdrew from the study and assuming that they did not engage in any key outcome. Significance was defined as p -values ≤ 0.05 . All analyses were conducted in Stata 14.

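### Does the SAP's definition of repeat testing demand four tests when only three kits are mailed?

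*SAP*

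**What the plan says.** Aim 2 in Protocol C.1 asks whether enhanced home testing "results in higher rates of (2a) any and repeat testing" than standard home testing. The Protocol does not define repeat testing. Its Planned Analyses paragraph (C.4) handles Aim 2a through the number of men with any home test and the mean number of tests per arm.

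The definition appears once, in the SAP's Analysis plan: "Repeat testing was defined as having tested at least twice in at least two of these intervals over the course of the study period". The intervals are three (baseline, 3 months, 6 months), and the preceding sentence justifies them as ones "which align with current CDC recommendations for HIV testing every 3-6 months among high-risk MSM".

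On supply, the overview in Protocol C.1 states that "3 HBST kits will be sent by mail at 3-month intervals over the course of 6 months", and C.4 (Experimental conditions) has the "test kits shipped to their homes 1-week after baseline, 3-months, and 6-months". The monthly survey is described in C.4 (Measures) as "inquiring about whether they used a study-provided HBST kits in the last month and what the result was".

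**The concern.** The sentence puts two thresholds side by side without saying how they combine.

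- **Reading A:** at least two tests within each of at least two intervals, so four tests or more.
- **Reading B:** at least two tests, falling in at least two different intervals.

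Grammar allows A, and A does not fit the design, because three kits cannot supply four tests. A man who did exactly what the study hoped, using each kit when it came, would be scored as not having tested repeatedly. Repeat testing is a named part of Aim 2a and has no other definition. A re-analyst who took A literally would therefore derive a different variable from one who took B, and with study kits alone would find no repeat testers in either arm.

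**Working it through.** The documents give no power calculation or stated figure for this outcome, so there is none to reproduce. The check has two parts: what each reading requires, and which reading the text supports.

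**Inputs**
- Kits per man: 3 (Protocol C.1 overview; C.4 Experimental conditions).
- Intervals: 3 (SAP Analysis plan).
- Follow-up: 7 months with monthly surveys (Protocol C.1 and C.4).
- Testing frequency cited by the SAP: every 3 to 6 months.

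**Tests required**
- Reading A: 2 tests x 2 intervals = 4, which exceeds 3 kits.
- Reading B: 1 test x 2 intervals = 2, which is within 3 kits.

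**Patterns of kit use.** Assume a kit can be used in the interval in which it is mailed, in any later interval, or never. Kit 1 then has 4 options (interval 1, 2, 3, never), kit 2 has 3 (interval 2, 3, never) and kit 3 has 2 (interval 3, never), so there are 4 x 3 x 2 = 24 patterns.

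- Reading A: 0 of 24, since no pattern contains four tests.
- Reading B with kit 3 used: 4 x 3 = 12 patterns. The 2 x 2 = 4 in which kits 1 and 2 are each used in interval 3 or not at all fail, leaving 8.
- Reading B with kit 3 unused: kits 1 and 2 must fall in different intervals. The pairs are (1,2), (1,3), (2,3) and (3,2), giving 4.
- Reading B in total: 8 + 4 = 12 of 24.

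If each kit is used in its own interval or never, there are 2 x 2 x 2 = 8 patterns. None meets A and 4 meet B (any two kits, or all three). The man who uses all three on schedule would need 2 tests from elsewhere to meet A.

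**A man who follows the cited frequency.** Suppose he tests with the first kit.
- Testing every 3 months puts tests near months 0, 3 and 6: three tests, one in each interval.
- Testing every 6 months puts tests near months 0 and 6: two tests, in the first and third intervals.

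Both men meet B and both fail A. A definition placed directly after that frequency is hardly meant to exclude men who keep to it.

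**Other pointers to B**
- The closing words of the definition set the whole study as the window for testing at least twice. Under A the window would already be each interval, and those words would add little.
- Entrants must meet the criterion "Have not been tested for HIV in the last year" (Protocol C.2). A bar of four tests in 7 months would be odd for men selected because they rarely test.
- Kit delivery and follow-up run once per interval: "This process will repeat for tests sent at 3 and 6 months" (C.4 Procedure).

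**What depends on the reading.** Only the repeat-testing variable does. It is not listed separately among the six key outcomes in the SAP. Any testing, the number of tests and the models of testing by interval do not use it.

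**The case for a change.** The best case for a change is that a definition should not have to be inferred. Under B the words requiring two tests are redundant, because tests in two intervals are already at least two tests; that makes A a natural grammatical reading. A looser reading, two tests at any time, is also what many people mean by repeat testing. It would add men whose tests all fell in one interval: as interval totals, (0,2,0), (0,0,2) and (0,0,3). Stating the rule would cost a sentence or two and a look at the existing variable.

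The redundancy is real, and the wording is not clean. The looser reading, however, ignores the explicit requirement of at least two intervals, so the sentence does not support it. The four-test reading would also reveal itself in use: with kits alone it gives no events in either arm, which an analyst would notice at once. It is not strictly unattainable, because section D.2 of the Protocol has men report tests taken at another clinic as well. Whether such tests count is a question about HIV testing rates in general and does not decide between A and B.

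The SAP is also written in the past tense, as an account of analyses done. Rewording it would not alter any derivation, and prescribing a replacement rule would go further than the documents, which imply B but do not state it.

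**Conclusion.** No change to the plan is needed. The sentence is ambiguous if lifted out of its paragraph: one reading needs 4 tests against 3 kits and is met by 0 of 24 kit-use patterns, while the other needs 2 tests and is met by 12 of 24. Read with the testing frequency cited just before it, the closing words of the definition and the schedule of one kit per interval, it means tests in at least two different intervals. This is loose wording that an analyst resolves sensibly.

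This conclusion rests on inference about intent, since the documents do not state the coded rule, and on the absence of any sign that the four-test rule was applied. The pattern counts assume kits may be used late or not at all; they say nothing about how often each pattern occurred. No effect on a result is shown. At most one exploratory outcome would be touched, in a 40-man pilot whose Planned Analyses paragraph calls the analysis mainly descriptive.

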
Figure 3. Timeline of study assessments

perceptions of “enhanced” HBST or HBST alone, additional procedures/services they might have preferred. Those in the “enhanced” condition will be asked about their impressions of counseling over the phone and the usability of the monitoring method. Participants will be paid \$20 for completing the baseline in-person appointment and \$15 per monthly assessment (\$105 total), with a \$55 bonus for completing all assessments on time (within +/- 5 days of being assigned).

Planned Analyses/Power Considerations. As this is a preliminary study, the primary goal is to explore evidence for the feasibility, acceptability, and utility of “active” monitoring and follow-up with HBST, as well as its effects on testing likelihood and frequency compared with usual HBST. As such, data analysis will be primarily descriptive. To address Aim 1, we will explore the number of successful phone contacts with those in the “enhanced” HBST condition, whether contacts involved counseling and/or referral, and qualitative data/ratings of acceptability, feasibility, and preferences. To address Aim 2a, we will compare the overall number of participants reporting any HBST use and the mean number of tests used across the conditions over the study period. To address Aim 2b/c, we will also compare the number of participants receiving HIV test counseling, referral for additional prevention services, and the number who successfully followed-up with these services. Finally, to address the secondary aims, we will compare mean frequencies of unprotected anal sex (condomless or without having taken PrEP that day) and mean levels of positive/negative affect, health empowerment, and social support by condition and testing status. We are aware of the limitations of relying on small scale studies for generating broad conclusions about the efficacy and/or effect sizes of interventions⁹⁶. As such, we are primarily interested in examining the pattern of results, rather than definitively testing hypotheses. We believe a sample size of 40 should allow some exploration of the direction of effects, while remaining within the scope of an exploratory project.

C.5. Human Subjects Involvement, Characteristics, and Design

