Participants will be recruited from the community using ads in popular gay social networking mobile apps (e.g., Grindr, Jackd, Scruff). Participants expressing interest in the study will be screened online. Those meeting eligibility criteria will be contacted by phone and email to schedule an in-person appointment to begin the study. Next, participants will complete baseline measures online. Then, participants will be randomized to a condition. For those in the "enhanced" condition, RAs will inform participants about the study's purpose and guide them in downloading study software onto their smartphones. Although participants will not need to actively provide any input through the app, RAs will instruct participants to keep the app installed, their Bluetooth sensor enabled, and their phones near them throughout the 7-month study. RAs will also ask participants to notify them as soon as possible if they lose their phone or get a new one, their data is erased, or if their service plan changes. Next, RAs will inform all participants that they should expect to receive an email each month with a unique link, and that clicking this link will allow them to complete their monthly assessments. They will also be informed that HBST kits will be mailed to them 1 week after their appointment, and then again in 3 months and 6 months, which they can choose to take or not. However, should they choose to do so, those in the "enhanced" condition will be told that they should expect a call from a QHTC associated with the study within 24 hours after opening their test, and that these calls are intended to provide counseling and referrals after taking the test (which participants can refuse). Finally, participants will be asked to complete a 30-minute follow-up interview about the study via phone after completing the study. They will be informed that they can pick up payments for completing study assessments at the research offices anytime during or after the study.

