provided by us or from another clinic) will be asked what the results of this test were. If it was reactive or positive, we will ask whether confirmatory testing has been completed or is pending and whether participants are currently under the care of a physician who is attending to these issues. For those noting having received a “reactive” result from a study test, who is not pursuing confirmatory testing and/or is not under the care of a physician who is aware of this issue, we will follow-up with these participants as soon as possible over the phone. The monthly assessment data will only contain participants’ unique study ID numbers, and will not be identifiable until it is downloaded and imported into the study databases. We will download and monitor the study monthly survey data every 48 hours, and for every participant with this constellation of responses, we will follow up with them over the phone to offer to make appointments with them for confirmatory testing and follow-up care.

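### The SAP sets withdrawn participants to no engagement in every model and names no second analysis, so if withdrawal differs by arm a reader cannot tell whether the direction of effect depends on that rule

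*SAP*

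**What the plan says.** The SAP's analysis plan starts from self-report: "Monthly survey responses were first aggregated across the entire study period". It then fits linear or Poisson models over the whole study, and GEE models over the three study intervals. For all of them, intent-to-treat means "retaining participants who withdrew from the study and assuming that they did not engage in any key outcome". The SAP does not say whether reports made before withdrawal are kept, or how missed surveys are handled for people who stay. It names no alternative analysis.

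In the Protocol, C.4 (Measures) has the monthly survey ask about use of study kits and, for each prevention service, "whether they sought each service over the last month". Section D.2 shows that the survey also reaches tests from outside the study; the wording there is "provided by us or from another clinic) will be asked what the results of this test were". C.4 (Planned Analyses/Power Considerations) is silent on withdrawal, missing data and sensitivity analysis. It describes the analysis as mainly descriptive and justifies the sample this way: "We believe a sample size of 40 should allow some exploration of the direction of effects".

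On differences between arms, C.5 says of the enhanced arm that "RAs will instruct participants to keep the app installed, their Bluetooth sensor enabled, and their phones near them throughout the 7-month study". The same section adds that the app needs no active input and that counselling on the calls can be refused. Late surveys are chased without regard to arm: "failing to do so within that time will prompt the RA to follow up via phone and email to encourage adherence".

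**The concern.** A zero for a withdrawn participant is an assumption, not an observation. A man who stops answering surveys may still have an STI test, be prescribed PrEP, test at a clinic, or use a kit he already has. For study kits not yet sent, the zero is correct if mailing stops at withdrawal, but the documents do not say whether it does.

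Applying one rule to both arms does not make it neutral. The arm that loses more people collects more assumed zeros. If some of those people did engage, the comparison generally moves toward the arm with better retention. With 20 per arm, a gap of three withdrawals can change the sign of a modest difference. Direction is what the Protocol says the sample is for. With a single analysis, nobody can see whether the reported direction comes from the data or from the zeros.

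**Working it through.** **Inputs.** From the documents: 20 per arm, three kits, monthly surveys over 7 months. The plan states no power, effect size, event rate or withdrawal rate, so there is no figure of its own to reproduce beyond 20 + 20 = 40. Assumed: all withdrawal rates (w), outcome rates (p), a within-person correlation of 0.2 between kits, and withdrawal unrelated to outcome within arm.

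**1. Binary outcome, whole record set to zero.** Expected difference = p1(1 − w1) − p0(1 − w0), with 1 = enhanced and 0 = standard.

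- No true difference (0.70 in both), withdrawal 20% vs 5%: 0.560 − 0.665 = −10.5 points. Withdrawal swapped: +10.5.
- True +10 points (0.80 vs 0.70), 20% vs 5%: 0.640 − 0.665 = −2.5. Withdrawal swapped: 0.760 − 0.560 = +20.
- The shift is not universal. It vanishes when p1w1 = p0w0. With 0.80 vs 0.60 and withdrawal 15% vs 20%, 0.68 − 0.48 = 0.20, the true value.
- Large effects are robust. With 0.80 vs 0.50 and 5% withdrawal in standard, the sign reverses only if enhanced withdrawal exceeds 1 − 0.50 × 0.95/0.80 = 40.6%.

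**2. Kit counts, no true effect.** The rule can be read three ways: A, the whole record is zero; B, zeros from withdrawal on, timing uniform over the three kits; C, as B but withdrawal only after kit 1. The fraction of kit use kept is 1 − w (A), 1 − 2w/3 (B) and 1 − w/2 (C). For study kits, B and C apply only if later kits are still mailed. Repeat testing is defined thus: "Repeat testing was defined as having tested at least twice in at least two of these intervals". I take this as a test in at least two of the three intervals, with use 0.7 per kit.

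| Withdrawal | Quantity | A | B | C |
|---|---|---|---|---|
| 10% vs 30% | Count ratio | 0.90/0.70 = 1.29 | 0.933/0.80 = 1.17 | 0.95/0.85 = 1.12 |
| 10% vs 30% | Repeat testing | 0.670 vs 0.521 | 0.688 vs 0.575 | 0.697 vs 0.601 |
| 10% vs 20% | Count ratio | 1.13 | 1.08 | 1.06 |
| 10% vs 20% | Repeat-testing gap | 0.074 | 0.057 | 0.048 |

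**3. Direction.** Simulation of 40,000 trials with true use 0.70 vs 0.60 per kit (ratio 1.17). The estimate points the wrong way in:

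| Withdrawal, better arm vs other | A | B | C | Observed intervals |
|---|---|---|---|---|
| 30% vs 10% | 63% | 47% | 38% | 17% to 19% |
| 20% vs 10% | 41% | 31% | 26% | 17% to 18% |
| 10% vs 30% | 4% to 6% across readings | | | |

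With no withdrawal the figure is about 14% to 15%. In the last row the error favours the better arm, so its advantage is overstated.

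**4. Equal withdrawal (20%), unrelated to outcome.** With use 0.85 vs 0.60 the count ratio stays 0.85/0.60 = 1.42 in every reading. The mean difference of 0.75 kits falls to 0.60, 0.65 and 0.68 (A, B, C). The any-use difference depends on the rates. Here 10.4 points becomes 8.3, 11.1 and 12.4; with use 0.40 vs 0.20, 28.3 points becomes 22.7, 25.8 and 27.3.

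**5. Services, ever over 7 months, no true effect, 10% vs 30% withdrawal.** True rate 20%: whole-record zeros give 0.180 vs 0.140, a gap of 4 points. With earlier reports kept (constant monthly hazard, 0 to 6 surveys before withdrawal) it is 0.189 vs 0.167, about 2 points. A true rate of 10% gives 2 or 1 points.

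**6. What a second analysis would show.** Suppose 13 of 16 retained in the enhanced arm tested, and 14 of 19 in the standard arm. Retained only: 81.3% − 73.7% = +7.6 points. Under the SAP rule: 13/20 − 14/20 = −5. Bounds: 13/20 − 15/20 = −10 to 17/20 − 14/20 = +15. A reader shown only the −5 would not know that its sign depends on the rule.

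**The case against.** The best defence is that this is an openly stated rule, applied alike in both arms of a small study that disclaims definitive tests. Several parts of that defence stand.

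- If withdrawers truly did not engage, the zeros are right and nothing is shifted. The same holds for later kits if mailing stops.
- The evidence for unequal withdrawal is thin. Only the enhanced arm has the app and the counsellor calls, but no active input is needed and counselling can be refused. Surveys arrive by email link, so switching Bluetooth off is not withdrawal. Reminders and payments are the same in both arms.
- Every magnitude rests on assumed rates. The large figures concern kit use, and the worst ones need more withdrawal in the better arm. For services, counselling, supplies and PrEP, which make up most of the SAP's key outcomes, a shift of 1 to 4 points is less than one participant in 20.
- The observed-interval analysis has its own assumption. At 10% vs 30% withdrawal it is closer to the truth only if withdrawers' kit use exceeds about 43% to 45% of stayers' use.

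None of this supplies the missing check. The rule can change the sign under modest imbalance, and neither document offers a way to see whether it did.

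**Conclusion.** The point holds as a conditional gap in robustness. If withdrawal differs by arm and some withdrawers engaged, the rule generally moves the comparison toward the arm that keeps more people, and no planned analysis would reveal it. On the assumed kit-use rates this can reverse a modest advantage or overstate it; for services it is small. The figures illustrate what could happen and are not estimates for this trial.

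A reader might infer more than the documents support:

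- That the trial's estimates are biased, or biased toward a particular arm. No withdrawal rates are given, and the app and calls could raise or lower retention.
- That the zeros distort every planned scale. Steps 1 and 4 show exceptions: the risk difference when rate times withdrawal is equal in the two arms, and count ratios under equal withdrawal.
- That false-positive rates are inflated. In simulation with no true effect at 10% vs 30% withdrawal, this depends on the model: 10% to 20% for a t test under random withdrawal, 2% to 15% for Poisson with default errors, and 3% to 6% for services. The point made here is about the direction of the estimate.

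This is a cheap improvement, of minor to moderate priority for an exploratory pilot.

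**What to change.** 1. As the main analysis, keep every outcome reported before withdrawal and apply the no-engagement assumption only to unobserved periods. State how missed surveys among stayers are treated and whether kits were mailed after withdrawal.
2. Beside it, report two checks. The first is a GEE on observed intervals from all randomised participants with at least one survey, with interval in the model. For counts, match exposure to the outcome: kit intervals observed for kit use, months surveyed for services. The second varies withdrawers' assumed engagement by arm from zero to the stayers' rate and says whether the direction changes. For example, with no true effect, 10% vs 30% withdrawal and reading B, the count ratio runs from 0.933 to 1.250 across the by-arm extremes.
3. Report withdrawal and survey completion by arm.

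No new data are needed. The SAP is written in the past tense, so this may be a re-analysis. In the simulated GEE, standard errors on observed intervals were about 7% to 8% larger (0.480 to 0.512 under B, 0.461 to 0.498 under C). The added GEE omits people with no survey and rests on an untestable missing-at-random assumption, so neither it nor the zero rule should be shown alone.
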